9.4 STATISTICAL ANALYSES

9.4.1 GENERAL APPROACH

- **Descriptive Statistics:** All numerical variables will be summarized using mean \pm standard deviation and median (minimum, maximum). All categorical variables will be summarized using frequency (in %).
- **Inference tests:** All proposed statistical tests are two-sided. A p-value <0.05 is considered statistically significant.
- **Covariates:** Covariates will be compared between groups (intervention vs. control) using two sample t-tests, or Wilcoxon rank sum tests if they are continuous variables, and Chi-square tests or Fisher's exact tests if they are categorical variables. Each of the continuous covariate variables will be assessed of its correlation to the primary endpoint, or each of the secondary endpoints using a Pearson's correlation coefficient or a Spearman's correlation coefficient. Similarly, each of the categorical covariate variables will be assessed of its association to the primary endpoint, or each of the secondary endpoints using an ANOVA model, or a Kruskal-Wallis test. A covariate showing a significant association to intervention, a significant correlation or association to the primary (or secondary) endpoint will be considered as the adjusting (controlling) covariate and will be added as adjusting independent variable in the statistical models proposed for primary and secondary analyses.
- **Model assumptions:** Primary and secondary endpoints will be inspected of normal distribution assumptions using the histogram plots. If the variable is noticeably right (or seldomly left) skewed, then a transformation variable will be used in the parametric models to ensure the assumption of normality is met. As an alternative approach, a generalized linear model will be proposed to the variable using a distribution assumption fitting the data properly.

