9.2 SAMPLE SIZE DETERMINATION

Sample Size Justification:

We plan to enroll (consent) up to 228 participants.

To account for an anticipated attrition rate of 16% per arm, the power analysis is based upon a sample size of 196 participants, or 98 participants per arm. From a similar previously published study, it was found the mean of days with symptoms was 70 days (equivalently the mean of SFDs was 98 days out of total 24 weeks or 168 days of observation), and the standard deviation was 43 days.⁵ The proposed sample size will provide 90% power to detect an effect size of 0.465, or a difference of 20 symptom-free days with a standard deviation of 43 days, using a two sample t-test.

Randomization Scheme:

The randomization will be stratified by site. Within each site, participants will be randomized in a 1:1 allocation to receive active HEPA filtration (intervention group) and inactive HEPA unit (control group). Permuted block randomization will be employed.

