## 6.5. Data Summary and Visualization

All numerical variables will be summarized using mean  $\pm$  standard deviation and median (minimum, maximum). All categorical variables will be summarized using frequency (%). The variables will be summarized using descriptive statistics overall and stratified by intervention groups (HEPA filtration versus control) as well as by sites. The variables will be compared between groups (HEPA filtration vs. control) using two sample t-tests; or Wilcoxon rank sum tests if they are numerical variables, and Chi-square tests or Fisher's exact tests if they are categorical variables. The choice of a t-test or a Wilcoxon rank sum test will depend on the empirical distribution of the tested numerical variable. The choice of a Chi-square test or a Fisher's exact test will depend on the sample size used in the test.

Under the study design of stratified randomization, it is unlikely to expect any significant association between baseline characteristics and the intervention effect. However, some of the

baseline characteristics could be associated with the endpoints. For a candidate covariate used in multivariate analyses, its correlation to the primary endpoint, or a secondary endpoint will be assessed using a Pearson's correlation coefficient or a Spearman's correlation coefficient when it is a numerical variable. When the covariate is categorical, its association to the primary endpoint, or each of the secondary endpoints will be assessed using an ANOVA model, or a Kruskal-Wallis test. A variable that is associated with the intervention and primary endpoint and secondary endpoints or the association is mentioned in the previous literature will be considered as the adjusting (controlling) covariate and will be added as adjusting independent variable in the statistical models proposed for primary and secondary analyses.

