### Multivariable analysis

Potential confounders will be adjusted for the impact of intervention effect on the SFDs using a multivariable GLMM. We will calculate adjusted point estimates (i.e., average SFDs) and respective adjusted 95% CIs for each intervention group and for the difference in average SFDs between the intervention groups. We will also report the adjusted p-value of the difference in point estimates between intervention groups.

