**7. Changes to SAP**

*Any changes to the statistical approaches described in protocol must be described here with justification.*

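### Protocol 9.4.1, protocol 8.1 and SAP 6.5 give three different data-driven rules for choosing adjustment covariates; a short fixed list would do better than any of them

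*Protocol*

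**What the plan says.** Three places govern which covariates enter the efficacy models.

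- **Protocol 9.4.1:** "A covariate showing a significant association to intervention, a significant correlation or association to the primary (or secondary) endpoint will be considered" for adjustment. This is a comma list with no conjunction between its first two items. The natural reading is that either kind of association is enough.
- **Protocol 8.1:** history is taken at the start and end of the study, and factors that turn out imbalanced between arms are controlled in the primary analysis. No significance criterion is given. The accompanying Table 4 contains both baseline items and items collected at about 26 weeks.
- **SAP 6.5:** "A variable that is associated with the intervention and primary endpoint and secondary endpoints or the association is mentioned in the previous literature" becomes an adjusting covariate. The first limb joins its conditions with *and*. The second limb, the literature, names no sources and no variables.

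Protocol 9.4.1 and SAP 6.5 both say the selected covariates go into the models for the primary and secondary analyses. SAP 6.5 also remarks that "it is unlikely to expect any significant association between baseline characteristics and the intervention effect", while allowing that baseline characteristics may be related to the endpoints.

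SAP 6.6.1 describes the hypothesis test under its univariate heading, with arm and site only, and protocol 9.4.2 has the same terms. A separate SAP paragraph then says "Potential confounders will be adjusted for the impact of intervention effect on the SFDs using a multivariable GLMM". Neither document says which result decides. SAP section 7 contains only its instruction, "Any changes to the statistical approaches described in protocol must be described here with justification", and no entry.

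**The concern.** An adjusted analysis is credible when its covariates are fixed before anyone can see how they move the estimate. Here the same data can yield different adjusted effects depending on which section is followed, and two of the rules have a specific weakness in a randomised trial.

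- **Endpoint screen (protocol 9.4.1).** The correlation is computed over both arms pooled. If the filter works, a covariate that by chance favours the active arm picks up correlation with symptom-free days through the treatment effect. It is then more likely to be selected, and adjusting for it removes part of the true effect. Pure noise covariates also enter.
- **Arm-association condition (statistical limb of SAP 6.5).** Randomisation makes arm association a chance event, so requiring it shuts out most real predictors. Those are the variables from which adjustment gains precision.

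At stake are precision, a small attenuation, and the reproducibility of the adjusted result.

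**Working it through.** **Plan's own figure.** Protocol 9.2 states: "The proposed sample size will provide 90% power to detect an effect size of 0.465, or a difference of 20 symptom-free days". The SD assumed there is 43 days, and each arm has 98. Protocol 9.4.1 sets the threshold: "All proposed statistical tests are two-sided. A p-value <0.05 is considered statistically significant".

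- Effect size: 20/43 = 0.465.
- SE of the difference: 43 × √(2/98) = 6.14 days.
- Power: Φ(20/6.14 − 1.96) = Φ(1.30) = 90%. The stated figure reproduces (exact t-test 90.0%).

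**Candidates.** SAP Table 2 lists 7 demographic, 11 environmental and 8 medical-history variables: 26. The screening threshold is taken as 0.05. SAP 6.5 gives none of its own, so the general 0.05 of SAP 6.1 is assumed there.

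**Statistical limb of the SAP rule.** The chance of entry is at most 0.05 × (power to detect the covariate–endpoint correlation r with n = 196). By Fisher's z, that power is about Φ(atanh(r) × √193 − 1.96).

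- r = 0.10: power 29%, entry 1.4%
- r = 0.15: power 56%, entry 2.8%
- r = 0.20: power 80%, entry 4.0%
- r = 0.30: power 99%, entry 5.0%

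This imposes arm and primary-endpoint association only. Requiring secondary-endpoint association as well would lower it further. The documents give no value of r.

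**Noise under the protocol rule.** A noise covariate passes (arm or one endpoint) with probability 1 − 0.95² = 9.75%. With 21 noise candidates, 21 × 0.0975 = 2.05 are expected to enter.

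**Simulation.** 20,000 trials per setting; 98 per arm, SD 43, true effect 20 days, linear model, independent covariates. Five of the 26 are real predictors, jointly explaining R² of the variance (r = √(R²/5), so 0.14 at 10% and 0.20 at 20%). The literature route is left out.

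| Rule | Power, R² = 0 | R² = 10% | R² = 20% | Shift in 20-day effect |
|---|---|---|---|---|
| Unadjusted | 89.9% | about 90% | about 90% | none |
| Protocol *or* screen | 88.0% | 90.2% | 92.9% | −0.40, −0.59, −0.48 day |
| SAP *and* limb | – | 89.6–89.9% (R² 10–20%) | see left | see below |
| Fixed list of the five | 89.2% | 92.3% | 94.6% | none |

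Closed-form check of the fixed list: the SE becomes 6.14 × √(1 − R²).

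- R² = 10%: SE 5.83, power Φ(20/5.83 − 1.96) = Φ(1.47) = 93%.
- R² = 20%: SE 5.49, power Φ(20/5.49 − 1.96) = Φ(1.68) = 95%.

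Other assumed numbers and strengths of predictors moved the *or* shift only between −0.30 and −0.59 day (1.5–3%). The *and* limb also attenuates, by roughly 0.15 to 0.27 day. With no true effect, every rule rejected 4.5–5.3% of the time.

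**Same trial, both rules** (4,000 trials per setting, true effect 20 days). The significance verdict differs between the *or* and *and* rules in 3.4%, 5.0% and 6.3% of trials at R² = 0, 10% and 20%. At R² of 10–20% the two estimates differ by a median of 1.4–1.8 days.

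**26-week items.** Suppose a late-collected covariate is affected by the filter only through symptoms and has within-arm correlation ρ with symptom-free days. Adjusting for it leaves 20 × (1 − ρ²): 18.2 days at ρ = 0.3 and 15.0 at ρ = 0.5 (ρ assumed). Protocol 8.1 does not rule such items out.

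**The case against.** The strongest reply is that the practical damage is small. Attenuation is at most about 3%. The protocol screen does no worse than no adjustment once some covariates are prognostic. The SAP limb at its worst leaves roughly the 90% power the trial was designed for. All of this stands, so the point rests on conflicting rules and missing pre-specification more than on bias.

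Several stronger readings are tempting but not supported:

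- *SAP 6.5 excludes real predictors about 96% of the time.* That holds only for the statistical limb and for r near 0.2. The same sentence admits variables through the literature, and protocol Table 4 is itself presented as a list of wheeze risk factors, so known predictors may well get in. The fair criticism is that this route is unspecified. Nor does SAP 6.5 say the literature choice is made after the data are seen; it gives no timing.
- *Only the protocol rule pulls the effect toward zero.* The *and* limb does so too, slightly.
- *The primary test is invalid.* Type I error is intact. If the univariate model in SAP 6.6.1 governs, covariate selection does not touch the primary test at all. The documents leave that open, because protocol 8.1, protocol 9.4.1 and SAP 6.5 all put covariates into the primary analysis.
- *26-week items will be adjusted for.* SAP Table 2 holds baseline items only. The gap is that protocol 8.1 does not exclude the later ones.

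The fixed-list powers also assume the list contains exactly the true predictors. A real list will gain less if its members are weakly prognostic.

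**Conclusion.** The concern holds as an inconsistency and a weak method. Three rules for the same models disagree, the literature route is open-ended, the deciding model is not named, and the departure from the protocol is unrecorded.

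Under the assumptions above, the *or* screen loses about 0.4 to 0.6 of 20 days, and 1 to 2 points of power when nothing is prognostic. The statistical limb of the SAP rule forgoes a gain from about 90% to 92-95% power when the listed covariates explain 10-20% of variance. These sizes come from a linear model with independent covariates. The SAP's log-link count model with random site was not simulated, and neither the number nor the strength of real predictors is given in the documents. The matter should be corrected, but it does not threaten the validity of the test.

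**What to change.** - Delete the significance screens in protocol 9.4.1 and SAP 6.5 and the imbalance trigger in protocol 8.1.
- Name in both documents a short list of pre-intervention covariates, chosen before unblinding and kept whatever their p-values. Examples are age at hospitalization, gestational age, previous wheeze, family history of asthma, level of respiratory support and daycare attendance. Add baseline PM2.5 for the PM2.5 endpoint: protocol 6.1.1 says it is collected to control for variability between homes, yet SAP Table 2 does not list it.
- Exclude items measured at 26 weeks from adjustment.
- State whether the unadjusted or the adjusted model decides the primary hypothesis.
- Keep baseline comparisons between arms as description only, and enter the change with its reason in SAP section 7.

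This costs wording and no new data. If none of the listed covariates proves prognostic, power falls by about 0.5 to 1 point (89.2% against 89.9% unadjusted in the simulation).

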9.4.2 ANALYSIS OF THE PRIMARY EFFICACY ENDPOINT

- **Primary Objective:** To test the efficacy of a HEPA filtration unit home intervention, relative to the control arm, with respect to respiratory symptom burden (as measured by symptom-free days; SFD) over 24 weeks following activation of filtration.
- **Primary Endpoint:** Number of caregiver-reported SFDs over 24 weeks following activation of filtration (SFD defined as a 24-hour period without coughing, wheezing, or trouble breathing)
- **Statistical Hypothesis:** Mean of SFDs in the HEPA filtration home intervention group is larger than mean of SFDs in the control group. The hypothesis testing is the comparison of superiority.
- **Statistical Procedures:** The hypothesis will be tested using a mixed effect model after accounting for within cluster correlation. The model uses the primary endpoint as the dependent variable, and the intervention effect (intervention vs. control) as the independent variable or the fixed effect with site as a random effect.
- **Missing Data:** The primary endpoint will be imputed if there is any missing observation in the ITT. The statistician will assess the missing patterns to determine if the cause of missing is missing at random (MAR), missing completely at random (MCAR), or missing not at random (MNAR). Imputation methods such as multiple imputation (MI) methods and pattern-mixture methods will be used in imputation and analyses.

9.4.3 ANALYSIS OF THE SECONDARY ENDPOINTS

- **Secondary Endpoint 1:** Caregiver reported unscheduled healthcare visits. The proposed statistical method will be a generalized mixed effect model. The dependent variable will be counts of unscheduled health care visits from each of the metrics or the sum of all metrics. Each variable of counts is considered to follow a negative binomial distribution and its log link will be used to connect the independent variable, or the fixed effect of intervention effect with site as a random effect.
- **Secondary Endpoint 2:** Total PedsQLTM Infant Scales score. The proposed statistical model will be a mixed effect model using Total PedsQL score as the dependent variable, the intervention effect as the fixed effect, with site as a random effect. Means (and SEs) of Total PedsQL score estimated from the mixed effect model will be presented in the final result and compared between groups through a p-value to reach a statistical conclusion of significance and superiority.
- **Secondary Endpoint 3:** PM2.5 levels. The proposed statistical model will be a mixed effect model using PM2.5 level as the dependent variable, and the intervention effect as the fixed effect, and site as a random effect. Means and SEs of PM2.5 level from the mixed effect model will be presented in the final result. A p-value of the difference of means between groups will be used to reach a statistical conclusion of significance and superiority.
- **Missing Data:** Missing data of secondary endpoint will be assessed of causes of missing and imputed in analyses, following the same methods proposed for the primary endpoint.

9.4.4 SAFETY ANALYSES

Safety Analysis: Any AE related to the study groups specific to child participant will be documented and summarized as overall and by study groups using aforementioned descriptive statistics (see “Descriptive Statistics” in Section 9.4.1 for details). Safety analysis and reports will be made as specified in the Data Safety and Monitoring Plan (DSMP).

9.4.5 BASELINE DESCRIPTIVE STATISTICS

See Section 9.4.1 for details.

9.4.6 PLANNED INTERIM ANALYSES

Interim Analysis: An interim efficacy analysis has been planned for this study when 50% of study participants (49 participants in both groups) have completed the follow-up period. We will employ Lan & DeMets' alpha-spending function together with O'Brien-Fleming boundaries to preserve the overall type I error rate at 0.05 and power at 90% in the final analysis. The boundaries and operating characteristics for the proposed analyses are provided in the table below. In the event that findings from interim analysis provide evidence in favor of futility, the study team may consider halting the study.

Analysis	Information fraction	Reject H_0 (Efficacy)	Overall α spent	Reject H_1 (Futility)	Overall β spent
Interim	0.50	$ z > 2.963$	0.0003	$ z < 0.200$	0.012
Final	1.00	$ z > 1.969$	0.05	$ z < 1.969$	0.102

9.4.7 SUB-GROUP ANALYSES

A stratified analysis of primary endpoint and secondary endpoints will be done: a) by site among those sites with ≥ 10 participants per study groups, b) by sex for those levels/categories of sex with ≥ 10 participants, and c) race-ethnicity for those levels/categories of race-ethnicity with ≥ 10 participants.

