**6.6.3. Additional Analysis**

Descriptive analysis will be conducted to compare baseline pre-intervention PM2.5 levels by demographics, environmental factors, and medical history for the common room and sleep space, respectively. The average or median pre-intervention hourly PM2.5 levels will be calculated for 1) all participants who have available PM2.5 data; and 2) participants who have at least four days of pre-intervention PM2.5 data. The demographics and baseline variables will include the infant's race, infant's ethnicity, rurality, parental education, the season of hospitalization, wood stove

use, use of central AC, type of cooking stove, presence of hood, use of hood while cooking, whether the participant infant attends daycare, number of other children in the home, number of other children in home attend daycare or school, any furry pets in the home, previous history of wheezing with colds or other illnesses, history of asthma, chronic asthma medication used before hospitalization, asthma medication with other breathing illnesses, and the highest level of respiratory support.

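### Subgroup analyses by site, sex and race-ethnicity have no interaction test and are missing from the SAP, so chance differences between strata can easily look like effect modification

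*Protocol*

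**What the plan says.** Protocol 9.4.7 states: "A stratified analysis of primary endpoint and secondary endpoints will be done". The factors are site, sex and race-ethnicity. The only condition is size. A site needs at least 10 participants in each arm, while a sex or race-ethnicity level needs at least 10 participants in all, with no minimum per arm.

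The general testing rule in Protocol 9.4.1 has no exception for subgroups: "All proposed statistical tests are two-sided" and "A p-value <0.05 is considered statistically significant". SAP 6.1 uses the same threshold. The models in Protocol 9.4.2 and 9.4.3 and in SAP 6.6.1 and 6.6.2 contain arm as a fixed effect, site as a random effect and, in adjusted versions, covariates. None has an arm-by-factor term. Neither document mentions an interaction or heterogeneity test, and no multiplicity rule or exploratory label covers the subgroups. Protocol 9.4.9 says there are no exploratory analyses.

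The SAP has no subgroup section. Its Additional Analysis section (6.6.3) reads "Descriptive analysis will be conducted to compare baseline pre-intervention" PM2.5 levels across participant characteristics, which is not a comparison of treatment effects. SAP 7 requires any change from the protocol's statistical approach to be described and justified there, and lists none.

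**The concern.** Whether the filter works differently in boys and girls is a question about the difference between two effects. A test in boys and another in girls each ask whether that stratum's effect is zero. Comparing their verdicts does not answer the first question, because strata of limited size often fall on opposite sides of 0.05 even when they share one true effect.

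At stake is what the trial can say about effect modification. Without a stated test, a significant result in one stratum beside a non-significant one in another has no proper reading, and the smallest strata allowed by the size rule give very imprecise estimates. The SAP's silence adds to this: an analysis promised in the protocol has no model, test or reporting rule.

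**Working it through.** **Inputs.** Protocol 9.2 gives the design values: "The proposed sample size will provide 90% power to detect an effect size of 0.465, or a difference of 20 symptom-free days". The SD behind this figure is 43 days, and the planning test is the two-sample t-test on 98 children per arm (196 in all). The two-sided 0.05 level is from 9.4.1. The documents give no sex split, race-ethnicity mix or site sizes, so those below are assumptions. The calculations use the protocol's own t-test planning model, not the mixed models planned for analysis.

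**The plan's figure.** SE = 43 × √(2/98) = 6.14 days. The noncentral t gives power 90.0%, so the stated 90% reproduces.

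**One common effect, tested separately by sex.** Assume a 50:50 split, 49 per arm in each sex.
- SE = 43 × √(2/49) = 8.69 days; power for 20 days = 62.5%.
- Exactly one sex significant: 2 × 0.625 × 0.375 = 46.9%.
- Both significant: 0.625² = 39.1%. Neither: 0.375² = 14.1%.
- At a 60:40 split, power is 70.6% and 52.9%, and exactly one is significant in 48.8%.

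**Strata at the size floor.** SE = 43 × √(2/n); the 95% CI half-width is t × SE.

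| Per arm | SE (days) | Half-width (days) | Power for 20 days |
|---|---|---|---|
| 10 (site floor) | 19.2 | 2.101 × 19.2 = 40 | 16.6% |
| 5 (a level of 10 in total, split evenly) | 27.2 | 2.306 × 27.2 = 63 | 10.0% |

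Randomization is stratified by site only (Protocol 6.3), so a level of 10 children need not split 5:5. Any other split gives a larger SE.

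**No true effect, one endpoint.** If the strata were independent, the chance of at least one p<0.05 is 1 − 0.95^k:
- k = 5: 22.6%
- k = 10: 40.1%

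The strata are not independent, since each child has one sex, one race-ethnicity and one site. A simulation with overlapping strata (3,000 trials per setting, normal outcomes, N = 196, assumed race-ethnicity mix 50/20/20/10%) gave 25% with no qualifying site and 37% with four.

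**How many sites qualify.** SAP 3.2 names 17 sites. An even spread gives 196/17 = 11.5 children per site, about 6 per arm, which is below the floor of 10.

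**The interaction test.** For sex at 50:50, SE = 43 × √(2/49 + 2/49) = 12.29 days (normal approximation).
- Power for a 20-day difference in effect: Φ(20/12.29 − 1.96) = Φ(−0.33) = 37%.
- Difference needed for 80% power: 12.29 × (1.96 + 0.84) = 34 days.
- Three interaction tests per endpoint instead of 5 to 10 stratum tests: 1 − 0.95³ = 14.3% chance of a false signal if independent.

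**The case against.** The protocol promises only a stratified analysis. It does not say that p-values will be reported by stratum or that any difference will be called effect modification, and no subgroup appears among the objectives or hypotheses. A reader might infer that chance differences will be presented as effect modification, or that a split verdict is the expected result when the effect is uniform. The documents do not support the first. The arithmetic for sex does not support the second: the two sexes agree in 53% of trials (39% both significant, 14% neither). That part of the objection stands, and the claim here is limited to a common and easily misread outcome.

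It is also fair that the number of strata and the sex split are not in the documents, that 5 per arm is a floor case, and that few or no sites may qualify, so sex and race-ethnicity carry most of the argument.

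Two further defences are weaker. The protocol's wording could, in isolation, mean a pooled estimate adjusted for strata, but the subgroup heading and the minimum size for each level make sense only if levels are analysed separately. A reader might also infer from the SAP's silence that these analyses have been dropped. SAP 1 says the SAP is to be read with the protocol, and SAP 7 records no change, so the documents do not establish that either. They leave the status of a promised analysis unclear.

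Finally, the interaction test has low power. That is true and should be stated, but it is not a reason to substitute tests of a different question.

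**Conclusion.** The point holds as an inexpensive improvement. The protocol plans analyses within levels of three factors with no test of whether the effect differs between levels, and the SAP neither specifies nor withdraws them. Under a uniform 20-day effect and an even sex split, exactly one sex is significant in about 47% of trials (49% at 60:40). With no effect, at least one of 5 to 10 strata reaches p<0.05 in roughly 23% to 40% of trials per endpoint; the number of strata is assumed, and independence is only an approximation. A sex or race-ethnicity level at the permitted minimum would have about 10% power and a confidence interval of about ±63 days, roughly three times the 20-day design difference. None of this touches the primary analysis.

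**What to change.** Add a subgroup section to the SAP, and bring Protocol 9.4.7 and 9.4.9 into line with it:

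- For each endpoint and each factor in turn, add an arm-by-factor interaction to the planned model. For site, use either a random arm-by-site term or a fixed interaction among qualifying sites, and say which.
- State the scale on which the interaction is read, since SAP 6.6.1 uses a log link while the design difference is in days.
- Report the interaction result with subgroup estimates and 95% confidence intervals.
- Base any statement of effect modification on the interaction alone, with no claims of significance within strata.
- Label the subgroup analyses exploratory.
- Apply the 10-per-arm minimum to sex and race-ethnicity as well as site.

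The cost is SAP and protocol wording and a few model terms, with no new data and no change to the sample size. Two downsides should be stated in the SAP. The interaction test is weak (about 37% power for a 20-day difference between sexes, about 34 days needed for 80%), so a non-significant interaction does not show that effects are equal. The per-arm minimum may also exclude some small race-ethnicity levels from separate estimates.
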